#### 4.9.1.5 Multiple Comparisons/Multiplicity

The multiplicity will be controlled by using a hierarchical ranking strategy in the following testing sequence. All tests will be conducted at a two-sided alpha level of 0.05. For the primary endpoint family, the 2 treatment arms will be compared against placebo using the hierarchical testing procedure, in which the olezarsen 80 mg treatment group will be compared to the placebo at the 2-sided alpha level of 0.05, if the comparison is statistically significant ( $p < 0.05$ ), then the olezarsen 50 mg treatment group is compared against the placebo at the alpha level of 0.05. If the comparison of the olezarsen 80 mg treatment group to placebo group is not statistically significant, then the comparison of the olezarsen 50 mg treatment group against placebo and all

secondary endpoints will be considered exploratory. The order of the testing on the secondary endpoints is outlined below. The endpoint ranked as first will be tested and the difference will be declared statistically significant if the p value is less than 0.05. In case that the difference for the first endpoint is statistically significant, the endpoint ranked as second will be tested, and the difference will be declared statistically significant if the p-value is less than 0.05. The testing will continue as long as the previously ranked endpoint is statistically significant. If the secondary endpoints are not evaluated as a part of the hierarchical testing procedure due to previously ranked endpoint was not statistically significant, the statistical tests will be reported and interpreted in a descriptive manner.

1. Primary endpoints family:

- Primary endpoint: Comparison of percent changes in fasting TG from Baseline to Month 6 between olezarsen 80 mg treatment group and placebo in the FAS
- Primary endpoint (not co-primary endpoint): Comparison of percent changes in fasting TG from Baseline to Month 6 between olezarsen 50 mg treatment group and placebo in the FAS

2. Secondary endpoints will be tested in the FAS according to the following sequence:

- Comparison of percent change in fasting TG from Baseline to Month 12 between olezarsen 80 mg and placebo group
- Comparison of percent change in fasting TG from Baseline to Month 12 between olezarsen 50 mg and placebo group
- Comparison of percent change in fasting apoC-III from Baseline to Month 6 between olezarsen 80 mg and placebo group
- Comparison of percent change in fasting apoC-III from Baseline to Month 12 between olezarsen 80 mg and placebo group
- Comparison of percent change in fasting apoC-III from Baseline to Month 6 between olezarsen 50 mg and placebo group
- Comparison of percent change in fasting apoC-III from Baseline to Month 12 between olezarsen 50 mg and placebo group
- Comparison of proportion of patients who achieve fasting TG < 150 mg/dL at Month 6 between olezarsen 80 mg and placebo group in the subgroup of FAS with baseline fasting TG < 500 mg/dL
- Comparison of proportion of patients who achieve fasting TG < 150 mg/dL at Month 12 between olezarsen 80 mg and placebo group in the subgroup of FAS with baseline fasting TG < 500 mg/dL
- Comparison of percent change in fasting VLDL-C from Baseline to Month 6 between olezarsen 80 mg and placebo group
- Comparison of percent change in fasting VLDL-C from Baseline to Month 12 between olezarsen 80 mg and placebo group
- Comparison of percent change in fasting VLDL-C from Baseline to Month 6 between olezarsen 50 mg and placebo group
- Comparison of percent change in fasting VLDL-C from Baseline to Month 12 between olezarsen 50 mg and placebo group
- Comparison of percent change in fasting non-HDL-C from Baseline to Month 6 between olezarsen 80 mg and placebo group

- Comparison of percent change in fasting non-HDL-C from Baseline to Month 12 between olezarsen 80 mg and placebo group
- Comparison of percent change in fasting non-HDL-C from Baseline to Month 6 between olezarsen 50 mg and placebo group
- Comparison of percent change in fasting non-HDL-C from Baseline to Month 12 between olezarsen 50 mg and placebo group
- Comparison of proportion of patients who achieve fasting TG < 150 mg/dL at Month 6 between olezarsen 50 mg and placebo group in the subgroup of FAS with baseline fasting TG < 500 mg/dL
- Comparison of proportion of patients who achieve fasting TG < 150 mg/dL at Month 12 between olezarsen 50 mg and placebo group in the subgroup of FAS with baseline fasting TG < 500 mg/dL
- Comparison of percent change in fasting HDL-C from Baseline to Month 6 between olezarsen 80 mg and placebo group
- Comparison of percent change in fasting HDL-C from Baseline to Month 12 between olezarsen 80 mg and placebo group
- Comparison of percent change in fasting HDL-C from Baseline to Month 6 between olezarsen 50 mg and placebo group
- Comparison of percent change in fasting HDL-C from Baseline to Month 12 between olezarsen 50 mg and placebo group
- Comparison of percent change in fasting remnant cholesterol from Baseline to Month 6 between olezarsen 80 mg and placebo group
- Comparison of percent change in fasting remnant cholesterol from Baseline to Month 12 between olezarsen 80 mg and placebo group
- Comparison of percent change in fasting remnant cholesterol from Baseline to Month 6 between olezarsen 50 mg and placebo group
- Comparison of percent change in fasting remnant cholesterol from Baseline to Month 12 between olezarsen 50 mg and placebo group
- Comparison of percent change in fasting apoB from Baseline to Month 6 between olezarsen 80 mg and placebo group
- Comparison of percent change in fasting apoB from Baseline to Month 12 between olezarsen 80 mg and placebo group
- Comparison of percent change in fasting apoB from Baseline to Month 6 between olezarsen 50 mg and placebo group
- Comparison of percent change in fasting apoB from Baseline to Month 12 between olezarsen 50 mg and placebo group
- Comparison of percent change in fasting ApoA-1 from Baseline to Month 6 between olezarsen 80 mg and placebo group
- Comparison of percent change in fasting ApoA-1 from Baseline to Month 12 between olezarsen 80 mg and placebo group
- Comparison of percent change in fasting ApoA-1 from Baseline to Month 6 between olezarsen 50 mg and placebo group
- Comparison of percent change in fasting ApoA-1 from Baseline to Month 12 between olezarsen 50 mg and placebo group
- Comparison of percent change in fasting LDL-C from Baseline to Month 6 between olezarsen 80 mg and placebo group

- Comparison of percent change in fasting LDL-C from Baseline to Month 12 between olezarsen 80 mg and placebo group
- Comparison of percent change in fasting LDL-C from Baseline to Month 6 between olezarsen 50 mg and placebo group
- Comparison of percent change in fasting LDL-C from Baseline to Month 12 between olezarsen 50 mg and placebo group
- Comparison of percent change in fasting total cholesterol from Baseline to Month 6 between olezarsen 80 mg and placebo group
- Comparison of percent change in fasting total cholesterol from Baseline to Month 12 between olezarsen 80 mg and placebo group
- Comparison of percent change in fasting total cholesterol from Baseline to Month 6 between olezarsen 50 mg and placebo group
- Comparison of percent change in fasting total cholesterol from Baseline to Month 12 between olezarsen 50 mg and placebo group
- Comparison of proportion of patients who achieve fasting TG < 500 mg/dL at Month 6 between olezarsen 80 mg and placebo in the subgroup of FAS with baseline fasting TG  $\geq$  500 mg/dL
- Comparison of proportion of patients who achieve fasting TG < 500 mg/dL at Month 12 between olezarsen 80 mg and placebo in the subgroup of FAS with baseline fasting TG  $\geq$  500 mg/dL
- Comparison of proportion of patients who achieve fasting TG < 500 mg/dL at Month 6 between olezarsen 50 mg and placebo in the subgroup of FAS with baseline fasting TG  $\geq$  500 mg/dL
- Comparison of proportion of patients who achieve fasting TG < 500 mg/dL at Month 12 between olezarsen 50 mg and placebo in the subgroup of FAS with baseline fasting TG  $\geq$  500 mg/dL
- Comparison of adjudicated acute pancreatitis event rate during the Treatment Period between pooled olezarsen treatment group and placebo
- Comparison of adjudicated acute pancreatitis event rate during the Treatment Period between pooled olezarsen treatment group and placebo in the subset of FAS with  $\geq$  2 events of adjudicated acute pancreatitis in 5 years prior to enrollment in FAS

#### 4.9.1.6 Interim Analyses

There is no interim analysis planned for the study.

#### 4.9.1.7 Examination of Subgroups

Subgroup analyses of the primary efficacy and applicable secondary endpoints will be made to assess consistency of analysis results over subgroups. The subgroups include but are not limited to:

- Baseline fasting TG  $\geq$  500 mg/dL vs. < 500 mg/dL
- Baseline fasting TG  $\geq$  200 mg/dL vs. < 200 mg/dL
- age groups (< 65,  $\geq$  65 years)
- race (White vs non-White)
- Sex (male, female)
- ethnicity (Hispanic or Latino vs. Not Hispanic or Latino)

- Baseline BMI (< 25, 25 to < 30, 30 to < 40, ≥ 40 kg/m^2)
- diabetic status (diabetic vs non-diabetic)
- Baseline Hemoglobin A1C (HbA1c): < 6.5 vs. ≥ 6.5
- Baseline background therapies (lipid-modifying therapy versus none; statins versus no statins; Fibrates vs. no Fibrates)
- Previous treatment with volanesorsen: Yes vs. No

#### 4.9.2 Primary Efficacy Variable

The primary efficacy variable is the percent change from Baseline to Month 6 (average of Weeks 25 and 27) in fasting TG.

##### 4.9.2.1 Primary Analysis

The primary efficacy analysis will take place after the last patient has completed the Week 53/ET visit and the database has been locked.

The primary analysis of the primary endpoint is to compare the percent change from Baseline to Month 6 in fasting TG between each olezarsen treatment group vs. placebo group using the FAS.

If patients have intercurrent event(s) before Week 25, e.g., treatment discontinuation, use of additional medication, changes in background or concomitant treatments, the Treatment Policy strategy will be implemented, the patients' assessments post intercurrent events will continue to be collected. All assessments including those post the intercurrent events will be utilized in the analysis. Patients with a missing TG value at Month 6 will have TG imputed, details are described in Section 4.9.1.4.

**The attributes and description of the estimands are provided in the tables below:**

Treatments	
 
• olezarsen 80 mg
 
• placebo
 

Participant Population	Patients with hypertriglyceridemia and atherosclerotic cardiovascular disease (ASCVD) (established, or at increased risk for), or with severe hypertriglyceridemia (SHTG) as defined by protocol eligibility criteria
Variable	Percent change from Baseline to Month 6 (average of Weeks 25 and 27) in fasting TG
Intercurrent events (ICEs) and strategies	
 
• Discontinuation of study treatment prior to Week 25 Treatment policy strategy
 
• Disallowed concomitant therapy/procedure prior to Week 25 Treatment policy strategy
 

Population-level summary	Difference in means of percent change between olezarsen 80 mg and placebo in the FAS
Description of estimand	The difference in means of percent change from Baseline to the Month 6 in fasting TG between olezarsen 80 mg and placebo (regardless of early treatment discontinuation, use of additional medication, or change in background or concomitant treatments) in patients with hypertriglyceridemia and ASCVD (established, or at increased risk for), or with SHTG

For each of the 100 imputed datasets obtained from Section 4.9.1.4, the percent change from Baseline to Month 6 in fasting TG will be compared between olezarsen treatment groups and placebo using an analysis of covariance (ANCOVA) model that assumes unequal variance with percent change from Baseline to Month 6 in fasting TG as the dependent variable, treatment group (olezarsen 80 mg, olezarsen 50 mg, or Placebo) as factor, and natural log-transformed baseline fasting TG as a covariate.

The pseudo SAS code of ANCOVA:

```

/*****
/* Note:
/* baseline = baseline TG
/* impute = the iteration number in the multiple imputation
/* trtpn = Treatment group: 0=Placebo, 1= olezarsen 50 mg, 2 = olezarsen 80 mg*/
/* pchg = percent change TG from baseline to Month 6
*****/

data TG; set TG;
    logbase = log(baseline); /* log transformed baseline*/
proc mixed data = TG;
    by impute;
    class trtpn;
model pchg = trtpn logbase/ ddfm=satterth;
    lsmeans trtpn/e diff cl;
    estimate 'olezarsen 50 mg vs Placebo' trtpn -1 1 0;
    estimate 'olezarsen 80 mg vs Placebo' trtpn -1 0 1;
run;

```

The model will provide an estimate of Least Squares (LS) Mean of percent change from baseline in fasting TG for each treatment group as well as the treatment differences relative to the placebo group and the corresponding standard error.

The estimates from the fitted models for each of the 100 imputed datasets will be combined to provide an overall estimate with corresponding CIs and p-value (Little and Rubin 2002). The following pseudo SAS code will be used to estimate corresponding CIs and p-value:

```

proc mianalyze data=diff;
    modeleffects estimate;
    stderr stderr;
run;

```

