### 10.2 Sample Size Considerations

With 33 patients in each olezarsen treatment group and 22 in the pooled placebo group, there would be an approximately 80% power to detect a 60% difference between each olezarsen treatment group and pooled placebo group at an alpha level of 0.05 (two-sided), assuming 60% reduction in the olezarsen treatment patients, no change in the placebo patients, and a common SD of approximately 73%. It is estimated that dropout rate is approximately 20%.

Approximately 152 patients will be enrolled in this trial to account for potential early dropouts and to facilitate general safety evaluations.

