### **10.6.3 Efficacy Analysis**

#### **10.6.3.1 Analysis of Primary Endpoint**

The primary analysis of the primary endpoint is to compare the percent change from Baseline to Month 6 in fasting TG between each olezarsen treatment group vs. pooled placebo group using an ANCOVA model in the FAS. The ANCOVA model will include the effects of treatment (olezarsen 80 mg, olezarsen 50 mg, or Placebo), and log-transformed baseline TG. If patients have intercurrent event(s) before Week 25, e.g., treatment discontinuation, use of additional medication, changes in background or concomitant treatments, the Treatment Policy strategy will be implemented, the patients' assessments post intercurrent events will continue to be collected. The missing TG value at Months 6 or 12 will be imputed using an imputation model that contains the following variables: baseline fasting TG, fasting TG at each post-baseline visits and the multiple imputation will be stratified by treatment group ([Schafer 1997](#); [Schafer 1999](#)).

The MCMC method will be used under the multivariate normality assumption to impute the missing values by treatment group. To conform to the multivariate normality assumption, baseline and post-baseline TG will be natural log-transformed before the imputation process, the data will be back transformed to create the imputed data set after the imputation.

The primary efficacy analysis will take place after the last patient has completed the Week 53/ET visit and the database has been locked. Details of the controlled access to the unblinded data will be outlined in the SAP and Unblinding Plan.

The following sensitivity analyses of the primary endpoint will be conducted to assess the robustness of the primary analysis result, and details of the analyses will be outlined in the SAP:

- The primary analysis described above will be repeated in the PPS.
- The primary analysis will be repeated in the subset of FAS with no missing TG value at baseline and Month 6.
- A nonparametric Wilcoxon rank-sum test will be performed on the percent change in TG from baseline to Month 6. Missing data will be handled using the same multiple imputation method as the primary analysis. The treatment difference will be assessed

using the Hodges-Lehmann estimator of the location shift and corresponding 95% CI. The analysis will be conducted in the FAS.

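### The SAP text for the primary ANCOVA specifies unequal variances, but the code printed with it fits one pooled variance

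*Combined protocol and SAP*

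**What the plan says.** SAP 4.9.2.1 fits the primary model in each of 100 imputed datasets, "using an analysis of covariance (ANCOVA) model that assumes unequal variance". Treatment is the factor and log baseline triglyceride (TG) the covariate. The program that follows is introduced as "The pseudo SAS code of ANCOVA". Its PROC MIXED step has BY, CLASS, MODEL, LSMEANS and ESTIMATE statements only, and the model line is "model pchg = trtpn logbase/ ddfm=satterth". There is no REPEATED or RANDOM statement. Results are pooled with "proc mianalyze data=diff", without an EDF= option.

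Protocol 10.6.3.1 names the model terms but not the variance structure: "The ANCOVA model will include the effects of treatment (olezarsen 80 mg, olezarsen 50 mg, or Placebo), and log-transformed baseline TG". SAP 4.13, which lists changes from the protocol, does not mention variances.

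The primary model is repeated in the per-protocol and completer analyses, the tipping-point analysis (SAP 4.9.2.2, Sensitivity Analyses 1, 2 and 4) and the Month 12 TG analysis (4.9.3.1). The copy-increment-from-reference (CIR) analyses (Sensitivity Analysis 5) also use ANCOVA. SAP 4.9.3.3 describes the other lipids as analysed similarly, restates the model terms and does not mention variances.

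The only SD in either document is the sample-size assumption of about 73%, common to all groups (protocol 10.2, SAP 4.12).

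**The concern.** Two programmers working from 4.9.2.1 could each claim to follow the plan and report different standard errors, confidence intervals and p-values for the primary endpoint. Leaving that choice open until after unblinding is an avoidable degree of freedom.

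The choice matters because allocation is unequal. Pooled placebo is the smallest group. Pooling weights the variance estimate towards the two larger olezarsen groups, while the contrast depends heavily on the placebo variance. If placebo is the more variable group, the pooled standard error is too small; if the olezarsen groups are more variable, it is too large.

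**Working it through.** **What the code fits.** Without REPEATED / GROUP=, PROC MIXED estimates a single residual variance. With one variance parameter, the Satterthwaite option returns the ordinary residual degrees of freedom: 152 − 4 = 148 for all randomised patients. The option does real work only if variances are arm-specific, as the sentence above the code says.

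**Inputs.** Of 152 patients, 76 go to each cohort and are split 3:1. That gives 57 on each dose and 19 + 19 = 38 on pooled placebo. The evaluable numbers in protocol 10.2 are 33/33/22.

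**The plan's own figure.** Protocol 10.2 reads "With 33 patients in each olezarsen treatment group and 22 in the pooled placebo group" and claims "approximately 80% power to detect a 60% difference". With SD 73, SE = 73 × √(1/33 + 1/22) = 20.09 and 60/20.09 = 2.99. Power is Φ(2.99 − 1.96), about 85% (83.4% from the noncentral t with 53 df). The stated 80% is slightly conservative, and the sample size is not at issue here. Under this common SD the two models agree: 95% half-widths are 40.0 points (pooled) and 40.5 (arm-specific).

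**Effect of unequal SDs.** Let r be the olezarsen/placebo SD ratio (an assumption), the same for both doses, with placebo SD set to 1, nO = 57 and nP = 38:

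- pooled variance = [2(nO − 1)r² + (nP − 1)] / [2(nO − 1) + (nP − 1)] = (112r² + 37)/149
- coded SE = √[pooled variance × (1/57 + 1/38)]
- correct SE = √(r²/57 + 1/38)
- coverage ≈ 2Φ(1.96 × coded SE / correct SE) − 1

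For r = 0.4, pooled variance = (17.92 + 37)/149 = 0.3686, coded SE = √(0.3686 × 0.04386) = 0.127 and correct SE = √0.02912 = 0.171. The ratio is 0.745.

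| r | coded SE / correct SE | coverage of nominal 95% CI |
|---|---|---|
| 0.4 | 0.75 | 86% |
| 0.6 | 0.84 | 90% |
| 0.8 | 0.92 | 93% |
| 1.0 | 1.00 | 95% |
| 2.0 | 1.22 | 98% |

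The SE ratios are nearly the same at 33/33/22. Simulating the ANCOVA there (5,000 runs per scenario) gave pooled coverage of 95.4% at equal SDs, 88.5% at r = 0.5, 85.8% at r = 0.4 and 98.2% at r = 2. Arm-specific variances gave 94.7–95.4%.

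The two doses can also err in opposite directions. With SDs of 100 (50 mg), 36.5 (80 mg) and 73 (placebo), the SE ratio is 0.88 for 50 mg and 1.22 for 80 mg.

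**Which direction is likelier.** Percent change cannot fall below −100%, and the imputation model treats TG as normal on the log scale. If log-scale spread is similar across arms, a 60% reduction leaves an olezarsen SD of about 0.4 × 73 = 29.2. Patients at placebo-like levels widen it again. If 20% have mean 0 and SD 73 and 80% have mean −60 and SD 29.2, the overall mean is −48 and the variance is 0.8(29.2² + 60²) + 0.2(73²) − 48² ≈ 2,324. The SD is then about 48, so r ≈ 0.66, with an SE ratio of 0.86 and coverage of about 91%.

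Simulated lognormal TG with a 60% effect gave coverage of 84–85% with everyone on drug and 91–94% with 20% off drug.

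**Effect on the primary decision.** With no effect and equal log-scale spread, the coded model rejected in 5.0–5.1% of simulated trials. At a 60% effect it rejected in 99–100%. At 33/33/22 with r = 0.4, half-widths are 24.2 (pooled) and 33.7 (arm-specific); both are well inside a 60-point difference.

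**The case against.** The tempting stronger reading is that the primary confidence intervals are too narrow. The documents do not support that as fact. Their only SD is common to all arms, under which the models agree, and no section says which arm is more variable. The ratios of 0.4 to 0.8 are assumptions, and a ratio above 1 reverses the direction. This part of the objection stands.

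The code is also labelled as a sketch and is visibly incomplete: no step creates the dataset passed to the pooling procedure, and the pooling step does not separate the two doses. The prose already names the intended model, so harm follows only if the final program copies the sketch. That is fair, but the sketch is the only operational statement of the primary model, and nothing ranks prose above code.

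A reader might also infer that type I error for the primary test is inflated. Under no effect with similar log-scale spread it is not. For lower-ranked lipids inflation is conditional: if a lipid had no mean effect but an SD ratio of 0.8 or 0.5, a 5% test would run at about 7.0% or 12.2%. The documents give no SDs for these lipids, and 4.9.3.3 gives no code.

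Finally, Sensitivity Analyses 3 (rank-based) and 6 (log ratio) depend less on this choice. They give some reassurance but do not settle which primary interval is reported.

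**Conclusion.** The contradiction in SAP 4.9.2.1 is real and nothing else in the documents resolves it. Following the code would misstate standard errors and interval coverage whenever arm variances differ. Too narrow is the likelier direction, because drug effect shrinks the spread of a bounded percent change and placebo is the smaller arm, but this rests on assumed SD ratios. The 86% figure supposes that all patients stay on drug; about 91–94% is the more relevant range given the planned 20% dropout, if those patients sit at placebo-like levels. The consequence is for reported intervals, tipping points and possibly tests of lower-ranked lipids. The primary significance decision is unlikely to change at the assumed effect.

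The missing EDF= option is minor. Without it, a 5% test runs at about 5.2% with 148 degrees of freedom, or about 5.5% at the 45–55 that arm-specific variances would give.

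**What to change.** Before database lock:

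1. Add `repeated / group=trtpn;` to the PROC MIXED code in SAP 4.9.2.1 so that it matches the text.
2. Carry the same line to the analyses that reuse the model: per-protocol, completer, tipping-point, CIR and Month 12 TG.
3. State the variance structure for the other lipids in 4.9.3.3.
4. Optionally, supply a complete-data df to PROC MIANALYZE through EDF=, and say how it is chosen across the 100 imputations, for example the average or minimum Satterthwaite df for each contrast.

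If a pooled variance is what the sponsor intends, the phrase in the text should be deleted and the choice justified.

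The cost is one line of code per analysis and a few words of SAP text. Intervals may become somewhat wider; at equal SDs and 33/33/22 the half-width rises only from 40.0 to 40.5 points.
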